#### 6.5.1.4 Characteristics of Solicited ARs

A descriptive summary of the day of onset and the duration of solicited ARs up to 7 days after study injection (with a toxicity grade of Grade 1 or greater), by treatment arm (as defined in Section 6.1) who experience the following will be presented:

Any solicited ARs,

Any solicited systemic AR,

Any solicited local AR,

Each individual solicited systemic and local AR

The onset of individual solicited AR is defined as the time point after injection (Section 6.1) at which the respective solicited AR first occurred. The duration calculation method is available in the Section 6.1 as well.

#### 6.5.1.5 Other solicited ARs summaries

A summary of solicited ARs persisting beyond 7 days after study injection (with a toxicity grade of Grade 1 or greater) by grades, including the number and percentage of participants, by treatment arm (as defined in Section 6.1) who experience the following will be presented:

Any solicited ARs,

Any solicited systemic AR,

Any solicited local AR,

Each individual solicited systemic and local AR.

Medications taken to prevent or treat pain or fever will also be presented.

## 6.5.1.6 Subgroup Analysis

Analysis of solicited ARs may be conducted for subgroups as defined in Table 4 of Section 6.1 for the following summaries:

Solicited ARs by Toxicity Grade

Characteristics of Solicited ARs

Solicited ARs persisting beyond 7 days

#### **6.5.2** Unsolicited Adverse Events

An unsolicited AE is any treatment-emergent AE reported by the participant that is not specified as a solicited AR in the protocol or is specified as a solicited AR in the protocol but starts outside the protocol-defined period for reporting solicited ARs (ie, for the 7 days after vaccination). Serious solicited AR events are also considered as unsolicited SAEs.

Unsolicited AEs include serious and nonserious AEs.

Potential unsolicited AEs may be medically attended (ie, symptoms or illnesses requiring a hospitalization, emergency room visit, or visit to/by a healthcare provider). The participants will be instructed to contact the site as soon as possible to report medically attended event(s), as well as any events that, though not medically attended, are of participant concern. Detailed information about reported unsolicited AEs will be collected by qualified site personnel and documented in the participant's records.

Unsolicited AEs that are not medically attended nor perceived as a concern by the participant will be collected during an interview with the participants and by review of available medical records at the next visit.

An unsolicited AE is defined as any event occurring during the study not present before exposure to IP or any event already present that worsens in intensity or frequency after exposure to IP.

A MAAE is an AE that leads to an unscheduled visit to an HCP. This would include visits to a study site for unscheduled assessments (eg, rash assessment or abnormal laboratory follow-up) and visits to HCPs external to the study site (eg, urgent care, primary care physician). An AESI is an AE (serious or nonserious) of scientific and medical concern specific to the Sponsor's product or program for which ongoing monitoring and immediate notification by the Investigator to the Sponsor is required and documentation is in the form of a case narrative. Such events may require further investigation to characterize and understand them.

All unsolicited AEs reported or observed during the clinical trial will be collected from start of study intervention through 28 days after injection. All AEs leading to study discontinuation,

MAAE, SAEs, and AESIs will be collected from the start of study intervention administration until through EoS or discontinuation from the clinical trial.

Unsolicited AEs will be coded according to Medical Dictionary for Regulatory Activities (MedDRA) version 26.0 or higher and presented by MedDRA system organ class (SOC) and preferred term (PT).

Analyses of unsolicited AEs will be provided (as defined in Section 6.1):

for up to 7 days after injection,

for up to 28 days after injection and

until Day 181/EoS visit unless otherwise specified.

SOC will be displayed in an internationally agreed order. PT will be displayed in descending order of frequency of the mRNA 1083 treatment group and then alphabetically within each SOC. When summarizing the number and percentage of participants with an event, participants with multiple occurrences of the same AE or a continuing AE will be counted once. Only the maximum severity/toxicity level will be presented in the severity/toxicity summaries, and the strongest relationship level will be presented in the relationship summaries.

For the by-severity summaries, the toxicity grade of a solicited AR (starts outside the 7 days protocol-defined period for reporting solicited ARs) will be mapped to a severity level of Mild/Grade 1, Moderate/Grade 2, or Severe/ $\geq$  Grade 3, and the maximum severity level in the case of multiple events will be presented.

The following listings containing individual participant AEs data will be provided:

Any unsolicited AEs,

Any treatment-related unsolicited AEs,

Unsolicited serious AEs,

Unsolicited serious treatment-related AEs,

Unsolicited severe AEs

Unsolicited AEs leading to discontinued from the study,

Unsolicited MAAEs,

Unsolicited AESIs.

Treatment-emergent AEs will be flagged in all data listings.

In addition, number of participants with occurrences of selected AEs of clinical interests identified by SMQ will be summarized up to 28 Days After Injection and Throughout the Study. SMQ will be summarized by PT, if applicable. Detailed description of SMQ is presented in Table 9 and Table 10. A listing of unsolicited AEs by SMQ will be provided.

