8.4.6. Solicited Adverse Reactions

Solicited ARs are a subset of AEs consisting of selected signs and symptoms that participants are asked to record/report. In this study, the solicited ARs are reactogenicity events. The term "reactogenicity" refers to the occurrence of transient adverse effects associated with vaccine administration. The eDiary will solicit daily participant reporting of ARs using a structured checklist (Section 8.3.7). Participants will record such occurrences in the eDiary on the day of study injection and 6 subsequent days, for a total of 7 days.

Study sites will distribute Sponsor-provided oral thermometers and rulers for use by participants to assess body temperature and injection site reactions, respectively, for recording solicited ARs in the eDiaries. Based on availability, smartphone devices may be provided to those participants who do not have their own device to use for eDiary activities.

Severity grading of reactogenicity will occur automatically based on participant entry into the eDiary according to the grading scales presented in Section 10.5 modified from the Toxicity Grading Scale for Healthy Adult and Adolescent Volunteers Enrolled in Preventive Vaccine Clinical Trials (DHHS 2007). All solicited ARs (local and systemic) will be considered causally related to dosing.

Any solicited AR that meets any of the following criteria must be entered into the participant's source document and must also be recorded in the participant's Reactogenicity eCRF:

- Solicited local or systemic AR that results in a visit to an HCP (MAAE; Section 8.4.8)
- Solicited local or systemic AR leading to the participant withdrawing from the clinical study or the participant being withdrawn from the clinical study by the Investigator (AE leading to withdrawal).
- Solicited local or systemic AR lasting beyond 7 days postinjection.
- Solicited local or systemic AR that otherwise meets the definition of an SAE.

Additionally:

- If a participant reported a solicited AR during the solicited period and did not record the event in the eDiary, the event should be recorded on the Reactogenicity page of the eCRF.
- If the event starts during the solicited period, but continues beyond 7 days after dosing, the participant should notify the site to provide an end date to close out the event on the Reactogenicity page of the eCRF.

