9.5.3. Safety Analyses

The safety analyses will be separately performed by Cohort A and B, respectively.

All safety analyses will be based on the Safety Set of each cohort, except summaries of solicited ARs, which will be based on the Solicited Safety Set of each cohort. All safety analyses will be provided by treatment group. Participants will be included in the treatment group corresponding to what they actually received.

Safety and reactogenicity will be assessed by clinical review of all relevant parameters, including solicited ARs (local and systemic events), unsolicited AEs, SAEs, AESIs, MAAEs, severe AEs, and AEs leading to withdrawal from study participation.

The number and percentage of participants with any solicited local AR, solicited systemic AR, and solicited AR during the 7-day postinjection follow-up will be summarized. A two-sided 95% exact CI using the Clopper-Pearson method will also be provided for the percentage of participants with any solicited AR. Solicited ARs and grades are defined in Section 10.5.

The number and percentage of participants with unsolicited AEs, SAEs, AESIs, MAAEs, severe AEs, and AEs leading to withdrawal from study participation will be summarized. Unsolicited AEs will be coded according to MedDRA and presented by MedDRA system organ class and preferred term.

Solicited ARs will be coded according to the MedDRA for AR terminology. The Toxicity Grading Scale for Healthy Adult and Adolescent Volunteers Enrolled in Preventive Vaccine Clinical Trials (DHHS 2007) will be used in this clinical study.

The number of events of unsolicited AEs, SAEs, AESIs, MAAEs, severe AEs, and AEs leading to withdrawal from study participation will be reported in summarization tables accordingly.

The analysis strategy for safety parameters is presented in Table 10. For all other safety parameters, descriptive summary statistics will be provided. Further details will be described in the SAP.

Table 10: Analysis Strategy for Safety Parameters

Safety Endpoint	Number and Percentage of Participants	Number of Events	95% CI
Any solicited AR (overall and by local, systemic)	✓	NA	✓
Any unsolicited AE	✓	✓	NA
Any unsolicited treatment-related AE	✓	✓	NA
Any SAE	✓	✓	NA
Any treatment-related SAE	✓	✓	NA
Any unsolicited AESI	✓	✓	NA
Any unsolicited treatment-related AESI	✓	✓	NA
Any unsolicited MAAE	✓	✓	NA
Any unsolicited treatment-related MAAE	✓	✓	NA
Any unsolicited severe AE	✓	✓	NA
Any unsolicited treatment-related severe AE	✓	✓	NA

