#### 3 STUDY ENDPOINTS

## 3.1 Primary Endpoints

#### **Cohort A Substudy (≥65 Years)**

GM level at Day 29 by HAI assay for influenza and by PsVNA for SARS-CoV-2.

Influenza: Percentage of participants with seroconversion, defined as a Day 29 post injection level ≥1:40 if Baseline is <1:10 or a 4 fold or greater rise if Baseline is ≥1:10 in anti-HA antibodies measured by HAI assay.

SARS-CoV-2: Percentage of participants with seroresponse, defined as a Day 29 post-injection level ≥4-fold rise if Baseline is ≥ LLOQ or ≥4×LLOQ if Baseline value is <LLOQ in the nAb values measured by PsVNA.

Solicited local and systemic ARs through 7 days after study injection.

Unsolicited AEs through 28 days after study injection.

MAAEs from Day 1 through Day 181 (Month 6) or EoS.

AESIs from Day 1 through Day 181 (Month 6) or EoS.

SAEs from the time of informed consent through Day 181 (Month 6) or EoS.

AEs leading to discontinuation from Day 1 through Day 181 (Month 6) or EoS.

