#### 6.5.2.1 Overview of Unsolicited AEs

An overall summary of unsolicited AEs, including the number and percentage of participants, by treatment arm (as defined in Section 6.1) who experience the following will be presented:

Any unsolicited AEs,

Any unsolicited serious AEs,

Any unsolicited AESI,

Any unsolicited AEs that are medically attended,

Any unsolicited AEs leading to study discontinuation,

Any unsolicited severe/≥ grade 3 AEs,

Any unsolicited AEs that are fatal.

The table will also include number and percentage of participants with unsolicited AEs that are treatment-related in each of the above categories.

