#### 6.5.2.2 AEs by System Organ Class and Preferred Term

The following summary tables of AEs will be provided by SOC and PT, sorting by frequency on the mRNA-1083 group, using frequency counts and percentages (i.e., number and percentage of participants with an event) and number of events by treatment arm (as defined in Section 6.1):

All unsolicited AEs,

All unsolicited AEs that are treatment-related,

All unsolicited serious AEs,

All unsolicited serious AEs that are treatment-related,

All unsolicited AESI,

All unsolicited AESI that are treatment-related,

All unsolicited AEs that are medically attended,

All unsolicited AEs that are medically attended that are treatment-related,

All unsolicited severe (grade  $\geq$  3) AEs,

All unsolicited severe (grade  $\geq$  3) AEs that are treatment-related,

All unsolicited AEs leading to study discontinuation,

All Unsolicited Non-Serious AEs,

Unsolicited Non-Serious Severe (grade  $\geq$  3) AEs.

All summary tables by SOC and PT will be provided up to 28 days after vaccine injection. In addition, all unsolicited AEs and SAEs summary tables will be provided up to 7 Days After Injection.

For all SAEs, AESIs, MAAEs, AE leading to discontinuation from the study, AE leading to death summary tables will also be provided through Day 181/EoS as well.

All unsolicited AEs and unsolicited treatment-related AEs will be summarized by SOC and PT for AEs with occurrence in  $\geq 1\%$  of participants in any treatment arm based on PT.

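### Nonserious solicited reactions (onset Days 1-7) that are medically attended or lead to withdrawal meet the protocol's MAAE or AE-leading-to-withdrawal rule but are left out of the tables for those two primary safety endpoints

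*SAP*

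**What the plan says.** **Classification.** Protocol 8.4.6 treats solicited ARs as a kind of AE and lists those that need extra recording. One entry is "Solicited local or systemic AR that results in a visit to an HCP (MAAE; Section 8.4.8"; another is "Solicited local or systemic AR leading to the participant withdrawing from the clinical study", which the protocol labels an AE leading to withdrawal. SAP 6.5.1 repeats both labels. These events "must also be recorded in the participant's Reactogenicity eCRF". Only events reported after Day 7 are directed to the AE page.

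**Endpoints.** For both cohorts, protocol Section 3 and SAP 3.1 list "MAAEs from Day 1 through Day 181 (Month 6) or EoS" as a primary safety endpoint, with a parallel entry for AEs leading to discontinuation. Neither is limited to unsolicited events.

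**Outputs.** Protocol Table 10 (Section 9.5.3) has a row for "Any unsolicited MAAE", and its withdrawal row carries the same limit. The SAP 6.5.2.1 overview has "Any unsolicited AEs that are medically attended". The SAP 6.5.2.2 tables by system organ class and preferred term include "All unsolicited AEs leading to study discontinuation". The MAAE and discontinuation listings in SAP 6.5.2 are also labelled unsolicited.

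**Bridge between the two.** The opening definition in SAP 6.5.2 admits a solicited term as unsolicited only if it begins outside the 7-day window. One exception follows: "Serious solicited AR events are also considered as unsolicited SAEs".

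**The concern.** Two primary safety endpoints are defined more widely than the tables meant to report them. A program built on the stated definition of an unsolicited AE would drop a nonserious solicited AR with onset in Days 1-7 from the MAAE or discontinuation count, even though the protocol calls that event an MAAE or an AE leading to withdrawal. No solicited-AR summary in SAP 6.5.1.1 to 6.5.1.6 has a medically attended or leading-to-withdrawal row to make up for it.

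The dropped events matter for interpretation because protocol 8.4.6 deems every solicited AR causally related to dosing. The report could also contradict itself on its face. Several Grade 4 reactions, such as headache and fatigue, are defined in protocol Appendix 5 by an emergency-room visit or admission, yet a participant with one could be absent from the MAAE table.

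**Working it through.** The plan states no figure on this point, so the check is a comparison of texts followed by an illustrative count.

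**Step 1: where each type of event is counted.**

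| Event | Counted in the MAAE or discontinuation tables? | Visible elsewhere? |
|---|---|---|
| Serious solicited AR, onset Days 1-7 | Yes, carried into the unsolicited set by SAP 6.5.2 | Solicited-AR tables |
| Solicited term starting after Day 7 | Yes, unsolicited by definition | Not applicable |
| Related unsolicited AE | Yes, SAP 6.5.2.1 adds treatment-related counts in each category | Not applicable |
| Nonserious solicited AR, onset Days 1-7, medically attended | No | By grade only (SAP 6.5.1.2) |
| Nonserious solicited AR, onset Days 1-7, leading to withdrawal | No | By grade, and in disposition by reason (SAP 6.2.1; the reason is listed in protocol 7.1) |

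The gap is the last two rows.

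**Step 2: two hypothetical participants.**
- Headache on Day 2, emergency-room visit, sent home, not judged serious. This is an MAAE under protocol 8.4.6, recorded on the Reactogenicity eCRF. It is not unsolicited under the opening definition and not carried over. It appears as a Grade 4 headache and in no MAAE table.
- Fever of 38.7°C on Day 2 with a visit to a physician. This is also an MAAE under protocol 8.4.6. It appears as Grade 2 fever, and its medical attendance is tabulated nowhere.

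**Step 3: texts that could close the gap.**
- *The Day 181 sentence in SAP 6.5.2.2* names MAAEs and discontinuations without the word unsolicited. It sits under the unsolicited heading and adds a further time period to the tables just listed, so it most naturally extends those tables.
- *The second definition of an unsolicited AE in SAP 6.5.2* takes in any event that is new or worse after injection. Read literally, it would include all new solicited ARs. The serious-AR carry-over would then be redundant. It would also clash with the rule in the same section that maps toxicity grades to severity only for solicited terms starting outside the 7 days.
- *Protocol 8.4.8* tells investigators to look through unsolicited AEs for MAAEs. That is a review instruction. The definition above it covers any AE that leads to an unscheduled healthcare visit, and 8.4.6 applies it to solicited ARs.

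None of the three brings these events into the tables, but the first two leave the SAP partly ambiguous.

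**Step 4: illustrative size.** The input from the documents is n = 2000 planned per arm (protocol Tables 4 and 5). The rate r of nonserious, medically attended solicited ARs with onset in Days 1-7 is not given and is assumed. Participants affected per arm = n × r:
- r = 0.05%: 2000 × 0.0005 = 1
- r = 0.5%: 2000 × 0.005 = 10
- r = 2%: 2000 × 0.02 = 40

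These are upper figures for the participant count at each rate, because anyone who also has an unsolicited MAAE is still counted.

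**The case against.** The strongest reply is that the SAP follows the protocol's own prespecified safety table, which says unsolicited for both rows, and that the conflict is only with labels inside a recording rule. Protocol 8.4.8 points investigators to unsolicited AEs when looking for MAAEs. The protocol 9.5.3 text and the SAP 6.5 introduction list MAAEs and withdrawal AEs as separate items alongside unsolicited AEs. The Day 181 sentence and the second definition can be read inclusively. On this view the matter is a minor clarification about showing one event in two tables.

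Part of this stands. The SAP is ambiguous in places, and much of the information is not lost. Grade 4 reactions defined by an emergency-room visit appear by arm in the toxicity-grade table, and reactogenicity withdrawals appear in disposition. The medical-attendance half of the point is therefore the stronger one, chiefly for lower-grade reactions with an office visit. Safety is also summarised descriptively, so no hypothesis test is affected.

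Agreement between Table 10 and the SAP does not, however, reconcile either of them with the endpoint and the classification rule. A grade table or a disposition row also does not count an event in the MAAE or discontinuation endpoint.

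It is also fair to object that the eCRF may not support the remedy. Protocol 8.4.6 requires these events on the Reactogenicity page but does not say that the page flags medical attendance. That has to be confirmed.

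**Conclusion.** The mismatch holds for a defined class: nonserious solicited ARs with onset in Days 1-7 that are medically attended or lead to withdrawal. Followed as written, the plan undercounts two stated primary safety endpoints in both cohorts. This rests on the opening definition in SAP 6.5.2 governing the tables, which is the reading that gives the serious-AR carry-over a purpose.

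Three stronger readings are tempting but not supported:
- *That the tables leave out vaccine-caused events in general.* Serious solicited ARs, solicited terms starting after Day 7 and related unsolicited AEs are all counted.
- *That many participants are missing.* No document gives the rate, so the undercount cannot be computed. The figure of 1 to 40 participants per arm rests wholly on the assumed 0.05% to 2%. The nearest information, in protocol 4.3, is a grade distribution at 30 µg rather than a rate of medical attendance at this trial's dose.
- *That the comparison between arms is biased.* One arm receives one active injection plus saline and the other receives two active injections, so reactogenicity could differ. Nothing in the documents shows that it does, or in which direction.

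**What to change.** 1. Extend the carry-over sentence in SAP 6.5.2 so that solicited ARs that are medically attended, or that lead to study discontinuation, are also counted in the MAAE and AE-leading-to-discontinuation summaries and listings. Show each as total, solicited and unsolicited.
2. Relabel the MAAE and withdrawal rows of protocol Table 10, and the matching rows in SAP 6.5.2.1 and 6.5.2.2, to agree.
3. Reconcile the two definitions of an unsolicited AE in SAP 6.5.2, and state whether the Day 181 tables use the same counting rule.
4. Confirm that the Reactogenicity eCRF data identify medical attendance and withdrawal for each event.

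The cost is wording and programming if step 4 succeeds, since protocol 8.4.6 already requires these events to be recorded. If the page does not identify them, source records would have to be used, and the cost cannot be judged from the documents. Reported rates would rise slightly, and the same event would appear in both a solicited-AR table and an endpoint table; a footnote handles that.

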#### 6.5.2.1 Overview of Unsolicited AEs

An overall summary of unsolicited AEs, including the number and percentage of participants, by treatment arm (as defined in Section 6.1) who experience the following will be presented:

Any unsolicited AEs,

Any unsolicited serious AEs,

Any unsolicited AESI,

Any unsolicited AEs that are medically attended,

Any unsolicited AEs leading to study discontinuation,

Any unsolicited severe/≥ grade 3 AEs,

Any unsolicited AEs that are fatal.

The table will also include number and percentage of participants with unsolicited AEs that are treatment-related in each of the above categories.

#### 6.5.2.2 AEs by System Organ Class and Preferred Term

The following summary tables of AEs will be provided by SOC and PT, sorting by frequency on the mRNA-1083 group, using frequency counts and percentages (i.e., number and percentage of participants with an event) and number of events by treatment arm (as defined in Section 6.1):

All unsolicited AEs,

All unsolicited AEs that are treatment-related,

All unsolicited serious AEs,

All unsolicited serious AEs that are treatment-related,

All unsolicited AESI,

All unsolicited AESI that are treatment-related,

All unsolicited AEs that are medically attended,

All unsolicited AEs that are medically attended that are treatment-related,

All unsolicited severe (grade  $\geq$  3) AEs,

All unsolicited severe (grade  $\geq$  3) AEs that are treatment-related,

All unsolicited AEs leading to study discontinuation,

All Unsolicited Non-Serious AEs,

Unsolicited Non-Serious Severe (grade  $\geq$  3) AEs.

All summary tables by SOC and PT will be provided up to 28 days after vaccine injection. In addition, all unsolicited AEs and SAEs summary tables will be provided up to 7 Days After Injection.

For all SAEs, AESIs, MAAEs, AE leading to discontinuation from the study, AE leading to death summary tables will also be provided through Day 181/EoS as well.

All unsolicited AEs and unsolicited treatment-related AEs will be summarized by SOC and PT for AEs with occurrence in  $\geq 1\%$  of participants in any treatment arm based on PT.

